## 9. TREATMENT EXPOSURE

### Analysis Set: FAS Set

Participant exposure to the protocol-specified treatments (IMP, malaria challenge agent, mandatory rescue medications - Riamet, Malarone, IV artesunate - and Primacain if also administered) will be listed and summarised by dose of IMP and overall.

## 10. PRIMARY ENDPOINT ANALYSIS (PK/PD ANALYSIS)

### Analysis Set: PK/PD Analysis Set

The primary endpoint is the PK/PD relationship of MMV367.

### 10.1 Overview of methodology for PK/ PD Modelling

Two stage approach:

1. Estimate the PK parameters by fitting a PK model and relevant covariates to the individual PK concentrations
2. Estimate the PD parameters by fitting a PKPD model to the asexual parasitemia observations using the individual PK parameters as regressors

### 10.2 Sources of Data

The PK/PD dataset will contain the individual information on the inoculum volume, date and time of its administration; doses of MMV367 administered with date and time of administration; plasma PK concentrations of MMV367 with date and time of blood sampling; triplicate total parasitemia counts by 18S qPCR with date and time of blood sampling; gametocytemia counts by pfs25, pfMGET and pfSBP-1 if relevant; and typical covariates such as age, body weight, height, sex and race.

The PK/PD dataset will contain the data from the current VIS study MMV\_MMV367\_22\_01 and from the past MMV\_MMV367\_21\_01\_FIH study.

The PK/PD dataset for MMV\_MMV367\_22\_01 will be prepared by SSR in the MMV format from the database. The PK dataset for MMV\_MMV367\_21\_01\_FIH will be prepared by ClinBay.

### 10.3 Data Assembly

#### 10.3.1 Master PK/PD dataset

Data from study MMV\_MMV367\_22\_01\_VIS will contain information on the individual MMV367 doses, MMV367 PK concentrations, the triplicated parasitemia levels, gametocyte data and typical covariates such as age, height, weight, sex and race. Data from study MMV\_MMV367\_21\_01\_FiH will be added to increase the number of individuals with PK profiles.

A master dataset will be assembled formatted according to the MMV dataset standard. (cf., "MS\_IQdataset\_V4"). Plasma concentration will be in ug/mL, total parasite levels in counts/mL, and doses in mg. Gametocyte data is in copies/uL.

Parasite data after the first administration of rescue medication is flagged by setting the IGNORE column to "Rescued". The time in hours is relative to the (first) MMV367 administration time. Gametocyte data will be converted to parasite counts following the

instructions in "Analyzing RNA data by [name] Nov2017.docx". Total counts of parasites were flagged to be ignored (by setting the column IGNORE to "gametocytes") if counts of gametocytes exceeded 10% of total counts.

A general analysis dataset will then be created from the master dataset. The general dataset will contain the following observations: MMV367 plasma concentrations, total parasite count, as well as counts of gametocytes. In addition, dosing records for *P. falciparum* inoculation, MMV367 administration and rescue medication administration will be defined.

The following covariates will be included as additional columns in the general dataset.

- DOSELEVEL: the dose amount
- DOSEMULT: the number of doses
- WT0: body weight (kg)
- AGE: age (years)
- SEX: sex (male or female)
- Infection status (for all participants from MMV\_MMV367\_22\_01\_VIS infection status will be positive; For all participants from MMV\_MMV367\_21\_01\_FIH infection status will be negative.)
- PLbase: The model baseline parasitemia value – the geometric mean of parasite counts at time of first MMV367 dose.

#### **10.3.2 PK modeling data set**

Observations below the lower limit of quantification (LLOQ) will be censored by setting the CENS column for these observation records to 1 and setting the corresponding dependent variable (DV) column to the LLOQ (→ M4 method). Observation records with missing values and records with missing times will be ignored. Records flagged to be ignored will be removed from the dataset. Observations not analyzed in the PK modelling (i.e., all parasite count records) will be removed. Consequently, the PK modelling NLME dataset will contain only MMV367 dosing records and MMV367 plasma concentration records.

#### **10.3.3 PD modeling data set**

Observations below the LLOQ will be censored by setting the CENS column for these observation records to 1 and the corresponding DV value to the LLOQ, i.e., 10 p/mL (→ M3 method). Total and viable counts of parasites for which counts of gametocytes exceeded 10% of total counts are flagged to be ignored (by setting the column IGNORE to "gametocytes"). Observation records with missing values and records with missing times will be ignored. Records flagged to be ignored will be removed from the dataset. Observations not analysed in the PD modelling analysis (i.e., MMV367 plasma concentration records) will be removed. Consequently, the PD modeling NLME dataset will contain only MMV367 dosing records and total parasite counts.

Parasite counts will be log-transformed for the PD modelling and estimated individual PK model parameters will be added to the dataset as regressors.

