Parasite regrowth following initial parasite clearance is required to effectively characterise PK/PD parameters such as the half maximum effective concentration (EC_{50}) of MMV367. A single dose of 20 mg is expected to result in initial parasite clearance in the IBSM model (\log_{10} parasite reduction ratio over a 48 h period [PRR_{48}] median 2.9, 95% CI: 0.26 - 5.8), but subsequent parasite regrowth is expected to occur. It is predicted that parasitaemia will return to the pre-dose baseline with a median of 7 days post-dosing (95% CI: 2.5 - 14). Additionally, modelling indicates that there is a 50% chance for a typical individual dosed with 20 mg to have a full parasitaemia profile above the lower limit of quantification (LLOQ) of the qPCR assay. Thus, a significant amount of data is expected to be generated at this dose level and three participants will be dosed with 20 mg MMV367 in Cohort 1.

Testing of 90 mg MMV367 is considered important because it is predicted to represent an “intermediate” dose level. That is, modelling indicates that 90 mg will result in faster parasite clearance (\log_{10} PRR_{48} median 3.6, 95% CI: 1.8 – 6.2) compared with 20 mg for a typical individual, while retaining a good chance of parasite regrowth occurring and thus contributing to refining the MMV367 EC_{50} estimate. Two participants will receive 90 mg MMV367 in Cohort 1.

Testing of 1500 mg MMV367 is required to characterise the PK/PD parameters across the full dose range, in particular the maximum killing rate (E_{max}). The chance of parasite regrowth occurring at this dose level is considered very low and thus data from this dose level will have a long duration of observable maximum killing rate ensuring a reliable estimation of the maximum clearance rate (E_{max}), however it is not anticipated to contribute to refining the estimate of the EC_{50} . Therefore, one participant dosed with 1500 mg is considered sufficient in the first cohort.

Dose selection for Cohort 2

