#### 11.1.2 Parasite clearance kinetics

The Parasite Reduction Ratio (PRR) and corresponding parasite clearance half-life ( $PCt_{1/2}$ ) of asexual parasites is derived from the clearance rate of parasitaemia after administration of MMV367 treatment. The analysis of PD response to investigational antimalarial therapy consists of:

- calculating the optimal parasite clearance rate (slope coefficient from the log-linear decay regression of qPCR data) for each individual, then,
- estimating dose specific parasite clearance rate and 95% confidence interval (CI) by calculating the weighted average slope estimate and corresponding standard error (SE) using an inverse-variance method.

The data used for all model selection and fitting calculations is comprised of the  $\log_{10}$  transformed geometric mean of parasitaemia per time point per participant up to the first time point all parasitaemia replicates are ND. If during initial parasite clearance there are no samples ND for a participant, the last time point included in the analyses will be three time points after the minimum observed parasitemia value. All subsequent time points are set to 'missing' regardless of whether parasitaemia values increased afterwards due to potential

recrudescence. Sensitivity analyses may be performed using other thresholds to determine parasite clearance, for example, but not limited to, the lower limit of quantification (LOQ) (i.e. the lower limit of the reportable range) of 32 parasites/mL or limit of detection of 111 parasites/mL [1], to assess robustness of PRR estimates.

The PRR per 48 hours,  $PRR_{48}$ , for asexual parasite will be estimated using the slope of the optimal fit of the log-linear relationship of the parasitaemia decay over time from MMV367 administration for each individual, as detailed in CTM QIMR SOP 41 and Marquart et al. [2]

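### The primary PD model censors 18S qPCR counts below an unsourced LLOQ of 10 p/mL, while SAP 11.1.2 gives the same assay an LOQ of 32 and an LOD of 111 parasites/mL

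*SAP*

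**What the plan says.** SAP 10.3.3 builds the dataset for the primary PD model. Counts below the limit are censored by "setting the CENS column for these observation records to 1 and the corresponding DV value to the LLOQ, i.e., 10 p/mL", with the M3 likelihood. It gives no source for the 10.

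SAP 11.1.2, on parasite clearance kinetics, names "the lower limit of quantification (LOQ) (i.e. the lower limit of the reportable range) of 32 parasites/mL or limit of detection of 111 parasites/mL" and cites the assay validation paper (SAP reference 1). These two figures are examples attached to an optional step: "Sensitivity analyses may be performed using other thresholds to determine parasite clearance". The main clearance analysis does not use them. It runs to the first time point at which every replicate is a non-detect, and non-detect replicates are set to 1 parasite/mL (SAP 11.1.1).

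Both analyses draw on one assay. The model takes "triplicate total parasitemia counts by 18S qPCR with date and time of blood sampling" (SAP 10.2), and the clearance analysis takes the "slope coefficient from the log-linear decay regression of qPCR data" (SAP 11.1.2).

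Protocol 4.3 relies on the assay limit without giving its value. It predicts a 50% chance for a typical participant given 20 mg "to have a full parasitaemia profile above the lower limit of quantification (LLOQ) of the qPCR assay".

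**The concern.** One named quantity, the lower limit of quantification of the 18S qPCR, is 10 in one section and 32 in another, and nothing in either document reconciles them. The stated LOD is also above the stated LOQ, the reverse of the usual order.

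Under M3 the limit is part of the likelihood. A censored record contributes the probability that the count lies below the limit; an uncensored record contributes a density at its value. A limit set too low for the assay can therefore do one of two things. It can claim more about a below-range result than the assay supports, or it can let counts outside the reportable range enter as ordinary measurements.

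Low counts fall at the end of the kill phase, at the nadir and at the start of regrowth. Protocol 4.3 says regrowth is needed to estimate EC50, and Protocol 9.4.2 derives MIC and PRR48 from the fitted model. The between-cohort review also uses PK/PD modelling to choose doses (Protocol 4.3 and 10.1.8). SAP section 10 plans no sensitivity analysis on the censoring limit.

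**Working it through.** **No plan figure to reproduce.** The 10 p/mL is asserted without derivation, so the check compares the stated limits and then sizes the difference.

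**Size of the disagreement**
- 32/10 = 3.2-fold, log10 = 0.51.
- 111/10 = 11.1-fold, log10 = 1.05.
- 111/32 = 3.5-fold, log10 = 0.54 (LOD above LOQ).

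All three limits are labelled per mL, and SAP 10.3.1 holds total counts per mL, so no stated unit difference explains the gap.

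**Samples affected during decay.** Inputs: predicted median log10 PRR48 of 2.9 at 20 mg and 3.6 at 90 mg (Protocol 4.3); parasitaemia of 5,000/mL at dosing (Protocol 2.2.1 and 4.2 expect it to exceed this), with 20,000/mL as an assumed higher value; PCR samples pre-dose and at 2, 4, 8, 12, 16, 24, 30, 36, 48, 54, 60 and 72 h.

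Time to reach a limit L from P0 = 48 h × log10(P0/L) / log10 PRR48. Example: 48 × log10(5000/10) / 2.9 = 48 × 2.699 / 2.9 = 44.7 h.

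| P0 per mL, dose | Limit 10 | Limit 32 | Limit 111 |
|---|---|---|---|
| 5,000, 20 mg | 44.7 h, 9 samples | 36.3 h, 9 | 27.4 h, 7 |
| 5,000, 90 mg | 36.0 h, 8 | 29.3 h, 7 | 22.0 h, 6 |
| 20,000, 20 mg | 54.6 h, 11 | 46.3 h, 9 | 37.3 h, 9 |
| 20,000, 90 mg | 44.0 h, 9 | 37.3 h, 9 | 30.1 h, 8 |

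Samples are those at or above the limit, pre-dose included. For 5,000/mL at 90 mg the 36 h sample sits on the limit of 10; counting it gives 9. Moving from 10 to 32 reclassifies 0–2 samples per participant, and moving from 10 to 111 reclassifies 1–2 (3 if that borderline sample is counted). Nadir and early-regrowth samples in the band are extra. A declining count spends 48 × 0.505/2.9 = 8.4 h between 32 and 10 at 20 mg, and 48 × 0.505/3.6 = 6.7 h at 90 mg.

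**Effect on the slope.** Simulated log-linear decay with an M3 fit, censored records coded <10 unless stated, the PCR times above, residual SD 0.25 on log10 (assumed), and baselines of 5,000 and 10,000/mL. Entries are mean estimated log10 PRR48.

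| How low results reach the dataset | True 2.9 | True 3.6 |
|---|---|---|
| Nothing numeric below 32 | 3.1–3.2 | 3.9–4.1 |
| Nothing numeric below 111 (worst case) | 3.7–4.2 | 4.9–5.3 |
| Hard limit of 32 or 111, coded at that same limit | 2.9–3.0 | 3.6–3.7 |
| Numbers reported down to 10 | 2.90–2.92 | 3.59–3.62 |
| As above, residual SD doubled below 111 | 2.81–2.82 | 3.56–3.57 |
| 111 read as a 95% per-replicate detection point (assumed), all-non-detect triplicates coded <10 | 2.98–3.01 | 3.64–3.66 |

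For scale, the protocol's predicted difference between 20 mg and 90 mg is 3.6 − 2.9 = 0.7 log10.

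**The case against.** A reader might infer that 10 is the wrong figure. The documents do not show that. The 32 carries a citation and the 10 does not, but the cited validation is not part of these documents. A Modelling Analysis Plan, named in Protocol 9 and not available here, may give the source of the 10.

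A reader might also infer that an LOD above an LOQ proves an error or a swap. SAP 11.1.2 glosses its LOQ as the bottom of the reportable range, which need not be a precision-based limit, so the two figures may follow different definitions. The order needs explaining but is not proof of a mistake. For the same reason, the strict conflict is 10 against 32. The 111 is a different quantity, and both 32 and 111 sit outside every main analysis.

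The strongest inference would be that the primary kill rate is biased upward. That requires that nothing numeric is reported below the true limit, and SAP 11.1.2 makes this doubtful. It offers 32 and 111 as alternatives to the all-non-detect rule; if the laboratory returned no numbers below one of them, that alternative would largely coincide with the main rule. With numbers reported down to 10, the simulation shows essentially no bias, or a slight downward one if low counts are noisier. The simulation is also a single log-linear decay without regrowth, so its figures do not transfer directly to EC50.

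These arguments limit the size and direction of the effect. They leave the contradiction in place: the SAP attaches two values to one limit of one assay, and the primary likelihood uses the one without a source.

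**Conclusion.** The point stands as an unresolved contradiction in a constant that the primary likelihood depends on. It does not stand as a demonstrated bias.

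If the reportable range ends at 32 as a hard cut-off, coding below-range results as <10 overstates log10 PRR48 by about 0.2–0.3 at a true 2.9 and 0.3–0.5 at a true 3.6. These sizes assume the simple decay model, the baselines and the residual SD listed above. A hard limit of 111 is a worst case that the SAP's own wording makes unlikely. If numeric values are reported down to 10, bias is negligible, but counts of 10–31 are modelled as uncensored although 11.1.2 places them below the reportable range. Following the SAP as written can therefore misclassify low counts at the nadir and in early regrowth, and the reader of the report would have no means of judging the effect.

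Confidence is high on the 10 versus 32 mismatch, and low on the size or direction of any effect until the laboratory's reporting rule is known.

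**What to change.** Before database lock:

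1. Take the LLOQ and LOD, with their definitions and volume basis, from the laboratory's validation report, and cite it in both SAP sections. Protocol 8.1.2 describes reporting per 500 µL of packed red cells while the SAP works per mL, so the basis should be explicit.
2. State how the laboratory reports non-detects and low numeric values.
3. Use the validated LLOQ as the M3 limit in SAP 10.3.3, with non-detects censored at the limit the assay supports. Use the same figures in 11.1.2, and correct or explain the order of LOD and LOQ.
4. Add a sensitivity fit of the final PD model at the alternative limits, reporting Emax, EC50, MIC and PRR48 under each.
5. Check whether the model supplied to the between-cohort review used 10, and record the answer.

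The cost is a text correction, one dataset constant and one additional analysis. If the limit rises, fewer low counts enter uncensored and relative standard errors may widen slightly.

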### **10.4. Methods**

#### **10.4.1. General PKPD model building approach**

Population models of the PK and PD will be developed in step-wise manner.

1. A population PK model will be developed to obtain individual PK parameter estimates based on which the individual PK profiles are well described.
2. A parasite growth model (parasite growth rate and deviation of parasitemia at inoculation from parasitemia at IMP administration) will be estimated from the total parasite counts before treatment administration. Estimation of typical and individual PD parameters will be performed with IQRtools SysFit. Other appropriate growth models, e.g. an oscillatory model, will be tested if advisable.
3. The PKPD model will be built using the individual PK parameter estimates and individual growth model parameter estimates as regression parameters. Estimation of typical and individual PD parameters will first be performed with IQRtools SysFit to investigate model identifiability and second with Monolix to additionally estimate IIV.

Estimations will be done using gradient-based SysFit algorithm in IQRtools or SAEM algorithm in Monolix. Other appropriate methods may be used if advisable.

Inter-individual variability (IIV) is implemented for normally distributed parameters using the following equation with  $\theta_0$  as population average parameter,  $\theta_i$  as individual parameter, and  $\eta_i$  as random effect that is distributed normally around zero ( $\eta_i \sim N(0, \omega^2)$ ).

$$\theta_i = \theta_0 + \eta_i$$

The following equation is used for log-normally distributed parameters.

$$\ln(\theta_i) = \ln(\theta_0) + \eta_i$$

Continuous covariates on log-normally distributed parameters will be implemented as follows.

$$\theta_i = \theta_0 \cdot \frac{COV_i^{\beta}}{COV_{median}} \cdot e^{\eta_i}$$

$\theta_i$  represents the individual parameter,  $\theta_0$  the population mean value,  $COV_i$  the individual covariate value,  $COV_{median}$  the population median covariate value,  $\beta$  the covariate coefficient, and  $\eta_i$  the individual random effect.

Categorical covariates on log-normally distributed parameters will be implemented as follows.

$$\theta_i = \theta_0 \cdot \sum_j (e^{\beta_j \cdot COV_{ij}}) \cdot e^{\eta_i}$$

The individual covariate values  $COV_{ij}$  are 1 if participant i belongs to the  $j^{\text{th}}$  category of the covariate and 0 otherwise.  $\text{beta}_j$  is the covariate value for the  $j^{\text{th}}$  category. For one category, i.e. the reference,  $\text{beta}_j$  is 0.

For the NLME modeling with Monolix, the log-likelihood and the Fisher information matrix will be approximated by importance sampling and stochastic approximation respectively. The number of iterations in the burn-in and the accumulation phase will be 500 and 200 respectively, but might be adjusted if required based on inspection of parameter estimate and objective function traces along estimation iterations. Individual parameters will be determined as conditional modes.

For PD modelling with the IQRtools SysFit implementation, a non-linear fixed-effects modelling approach is employed. Typical and individual parameters are both treated as fixed effects. The parameterization of individual parameters and covariates is fully consistent with the NLME parameterization above. The variances  $\omega^2$  of NLME random effects are accounted for by quadratic priors, added to the log-likelihood function, where the values for  $\omega^2$  are fixed and the  $\eta$  parameters are estimated. The profile-likelihood method [4, 5] is used to compute confidence intervals of the parameters estimated with the SysFit approach.

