#### 10.4.2. *Building a PK model*

The PK of MMV367 will be modeled using compartmental models describing the absorption after oral administration, distribution between central and peripheral compartments, and the elimination from the central compartment. The visual data analysis will guide the selection of models that will be tested (e.g., with respect to number of compartments, linear or saturable elimination, absorption kinetics and error model). Covariates will be included if appropriate. Estimations will be done using SAEM algorithm in Monolix. Other appropriate methods may be used if advisable.

FIH data from MMV\_MMV367\_21\_01\_FIH has previously indicated that MMV367 PK is adequately described by a one-compartment model with first order absorption parameterized in terms of  $CL/F$ ,  $Vc/F$  and  $ka$ . Therefore, this structural model will initially be used to model MMV367 PK using the PK modeling dataset. If required to adequately describe MMV367 PK, structural models with greater numbers of compartments and different absorption models (eg first-order rate, lag, transit compartments) will be fitted.

An exploratory investigation of covariate-parameter relationships will be undertaken during the PK modelling step. The covariate WT0 on the clearance and volume parameters will be included to allow predictions in children. Since the body weight distribution may be narrow, the exponents will be fixed to 0.75 and 1 respectively on clearances and volumes of distribution. Other covariates of interest may include AGE, SEX, Infection status and PLbase – however, depending on the population make-up of these covariates, some may not be included. In the event that the distributions of WT0 and AGE are very narrow, a reference value for the population may be used instead of individual participant covariates.

Covariate modeling will be undertaken in the following steps:

- Pre-defined covariate-parameter relationships will be identified based on exploratory analysis and mechanistic plausibility – in particular, WT0 on clearance and volume PK parameters (central and peripheral compartments, if appropriate).
- A full model will be constructed, avoiding simultaneous inclusion of covariates with correlation coefficients  $>0.5$ .
- Population parameters will be estimated (both fixed effects [covariate coefficients and structural model parameters] and random effects).

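### As printed in SAP 10.4.1, the categorical covariate equation contradicts the SAP's own definitions, and the continuous one is not centred at the median; both need correcting and a code check

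*SAP*

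**What the plan says.** SAP 10.4.1 gives two equations for covariates on log-normally distributed parameters.

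- Categorical: "\theta_i = \theta_0 \cdot \sum_j (e^{\beta_j \cdot COV_{ij}}) \cdot e^{\eta_i", in which the term under the summation sign is "j (e^{\beta_j \cdot COV_{ij". The indicators "are 1 if participant i belongs to the" category in question and 0 otherwise. The text then sets the coefficient to zero: "For one category, i.e. the reference". The reference is therefore one of the terms in the sum.
- Continuous: "\theta_i = \theta_0 \cdot \frac{COV_i^{\beta}}{COV_{median}} \cdot e^{\eta_i". The symbol θ₀ is called "the population mean value".

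For body weight, SAP 10.4.2 says "the exponents will be fixed to 0.75 and 1 respectively on clearances and volumes of distribution". The same section lists age, sex, infection status and baseline parasitaemia as covariates that may be added. SAP 10.4.1 states that the SysFit parameterisation matches the mixed-effects one. SAP 10.5 makes the typical PK and PD parameter values, with 90% confidence intervals, a PK/PD endpoint.

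**The concern.** A covariate multiplier has to equal 1 at the reference point: the reference category, or the median of a continuous covariate. Only then is θ₀ the typical value and exp(β) the ratio between a category and its reference. Neither printed equation meets this condition in general. The categorical one fails it for every value of β, and the continuous one for every β other than 1.

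This matters because typical PK values are reported as an endpoint, and SAP 10.4.2 judges the clinical relevance of covariates from the full-model estimates. It also includes weight so that predictions can be made in children. A table of θ₀ and β that does not mean what the text says it means can be misused by the next reader, even when the underlying fit is sound.

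**Working it through.** The plan gives no figure that depends on these equations, so there is nothing of its own to reproduce. The check evaluates the printed forms against the SAP's definitions.

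**Categorical.** Inputs from SAP 10.4.1: indicators 0 or 1, and β = 0 for the reference.

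- Two categories, reference participant: exp(0) + exp(β × 0) = 1 + 1 = 2.
- Two categories, other participant: exp(0) + exp(β) = 1 + exp(β).
- Ratio implied by the printed form: (1 + exp(β))/2. For exp(β) = 0.70 this is 0.85; for 1.30 it is 1.15.
- In reverse, a true ratio r is fitted as exp(β) = 2r − 1. So r = 0.8 gives 0.6, r = 0.7 gives 0.4, and r = 1.5 gives 2.0. For r of 0.5 or less there is no solution.
- With J categories the reference multiplier is J.

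Under `exp(sum_j beta_j × COV_ij)` the reference multiplier is exp(0) = 1 and the other category's is exp(β), as the definitions require.

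**Continuous, fixed exponent.** Inputs: exponents 0.75 and 1 from SAP 10.4.2. The median weight is not in the documents; I assume 60 to 85 kg (Protocol 5.1 requires at least 50 kg).

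The printed multiplier at the median is median^β / median = median^(β − 1).

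| Median weight (kg) | Multiplier, β = 0.75 | θ₀ / typical CL/F | Multiplier, β = 1 |
|---|---|---|---|
| 60 | 0.359 | 2.78 | 1 |
| 70 | 0.346 | 2.89 | 1 |
| 75 | 0.340 | 2.94 | 1 |
| 85 | 0.329 | 3.04 | 1 |

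The printed form divided by the standard form is the same at every weight: 0.340 at 50, 60, 75, 90 and 100 kg with a median of 75 kg. The difference is a constant that θ₀ absorbs.

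**Continuous, estimated exponent.** If a covariate such as age is added with β estimated, the printed form on the log scale is log θ₀ − log(median) + β log(COV). This is a regression on an uncentred covariate. In a simple log-linear approximation, the error correlation between log θ₀ and β has magnitude mean(x)/√mean(x²), where x = log age. For any distribution on 18 to 55 years (this study's limits, assumed for the first-in-human participants too), the minimum is 2√(ln 18 × ln 55)/(ln 18 + ln 55) = 2√(2.890 × 4.007)/6.898 = 0.987. SAP 10.4.1.1 asks for estimation-error correlations below 0.95, which I read as a limit on magnitude.

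**Does the fit itself change?** Both forms were fitted by least squares to one simulated clearance data set. Its inputs are assumptions: 37 uninfected and 18 infected participants, a true infection ratio of 0.70, a weight exponent of 0.75 and a median weight of 75.4 kg.

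- Standard form: θ₀ = 8.01, exp(β) = 0.705.
- Printed form: θ₀ = 11.81, exp(β) = 0.410, implied ratio (1 + 0.410)/2 = 0.705.
- The θ₀ values differ by the expected factor, 75.4^0.25 / 2 = 1.473.
- Largest difference in residuals: 3 × 10⁻¹⁰.

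The individual predictions are the same; only θ₀ and β change.

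**The case against.** The strongest reply is that these are typesetting slips with a clear intended meaning. A lost bracket round the fraction, or a sum that dropped out of the exponent, would produce exactly these forms, and text extracted from a PDF can itself move an exponent. That carries weight for the continuous equation, where the page should be checked before it is called an error. It carries less for the categorical one, where brackets enclose the whole exponential inside the sum.

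A reader might also infer more than the documents support:

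- *That typical CL/F and the infection effect are misstated.* No results or model code are shown, and Protocol 9.4.2 leaves full modelling details to a separate Modelling Analysis Plan. The harm is conditional. Infection status is also only a candidate covariate and may never be estimated.
- *That the primary PK/PD relationship is biased.* The PD step takes individual PK parameters as regressors. These do not change for weight, nor for a two-category covariate whose ratio to the reference exceeds 0.5.
- *That paediatric predictions fail.* Fitting and predicting with the same equation gives the same answer at any weight. Clearance is overpredicted only if θ₀ from the printed form is put into the standard allometric formula.
- *That half-life would be reported as about 5.8 h (17 h × 0.340) instead of 17 h.* The half-life endpoint is non-compartmental (SAP 11.2), so it does not use θ₀. A discrepancy in CL/F of that size should also be caught by the plausibility check in SAP 10.4.1.1 and by the non-compartmental CL/F.
- *That strong reductions can never be represented.* The 0.5 limit depends on which category is the reference, and the SAP does not say.

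**Conclusion.** The point stands in conditional form. The categorical equation, as printed, is inconsistent with the SAP's own indicator coding and zero reference coefficient: the two-category reference multiplier is 2, and exp(β) is not the category ratio. The continuous equation, if the typeset page matches the extracted text, inflates θ₀ for CL/F about 2.8 to 3.0 times at an assumed median weight of 60 to 85 kg. It leaves V/F alone, and it leaves any covariate with an estimated exponent uncentred.

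If the equations are coded literally, or the outputs are read under the standard form, the tabulated typical values and covariate effects would be wrong. The concentration-effect estimates would not be, within the limits given above. The correction should be made because typical values are a stated endpoint, but the documents do not show that any estimate is wrong.

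**What to change.** In SAP 10.4.1, after checking the typeset page, print the equations as:

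- Continuous: `theta_i = theta_0 × (COV_i / COV_median)^beta × exp(eta_i)`
- Categorical: `theta_i = theta_0 × exp(sum_j beta_j × COV_ij) × exp(eta_i)`

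Name the reference category for each categorical covariate. Confirm that the Monolix and IQRtools SysFit code uses these forms, and that the Modelling Analysis Plan prints the same ones. The cost is two equations and a code check, with no effect on trial conduct or data collection.
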